**Table 7-3 Pregnancy outcome follow-up checklist variables**

| Variable                              | Data captured   |
|---------------------------------------|---|
| Medications taken by the mother       | Name, dose, route of administration, start/stop, trimester of exposure  |
| Prenatal test                         | Name, date, abnormal (Yes/No/Not available), result (free text)   |
| Pregnancy outcome                     |   |
| Live birth                            | Date of birth, Gestation weeks at birth
Timing: full-term vs. premature vs. post mature
Normal (yes/no)
Neonate demographics (at birth):
Gender, weight (kg/lb and percentile),
Length (cm/in and percentile),
Head circumference (cm/in and percentile)
Small for gestational age*** (Yes/No)
Apgar Score 1min, 5min and 10 min
Infant status (alive/deceased)
Date of death
Cause of death |
| Termination                           | Date, Gestation weeks
Type: spontaneous abortion/miscarriage vs. induced termination
(therapeutic reason vs. elective termination)
Medical problem: Blighted ovum, molar pregnancy, ectopic pregnancy, Other
(free text)  |
| Stillbirth                            | Date, Gestation weeks
Autopsy (Yes/No/Unknown), free text  |
| Anomalies in the baby or fetus        | Anomaly notes (yes/no/unknow)
Description (free text)
Anomaly of known origin (No/Yes specify)
If least one major anomaly (Yes/ No only minor/ None /Unknown)  |
| Complication during or after delivery | None vs. Intrauterine death vs. Other specify   |

\*\*\* Yes, if the birth weight is <10th percentile for the GA ([Battaglia and Lubchenco 1967](#))

Low birth weight will be derived based on the weight at birth. If the weight is <2500g (i.e. 5 pound and 8 ounces) this will be considered low ([Cutland C et.al., 2017](#)).

Pregnancy and fetal/infant outcomes that are defined according to Manual of Argus Processing (MAP) are listed in [Table 7-4](#) and [Table 7-5](#). These will be used in the tabulations and analyses of primary or secondary outcomes.

**Table 7-4 Definition of key pregnancy outcomes**

| Outcome                                | Definition   |
|--|--|
| Full-term live birth                   | The patient gives birth to live neonate between 37 and 42 completed weeks of gestation.  |
| Premature live birth **                | The patient gives birth to a live neonate before 37 completed weeks of gestation.  |
| Post-mature live birth                 | The patient gives birth to a live neonate after 42 completed weeks of gestation  |
| Elective termination **                | Termination of pregnancy due to choice of mother of an otherwise normal fetus.   |
| Therapeutic termination                | If an abortion procedure occurs due to abnormal fetus, fetal death or risk to the mother.  |
| Spontaneous abortion **                | The fetus is spontaneously aborted (prior to 22 weeks gestation); prior fetal status via prenatal testing may or may not be known.   |
| Stillbirth **                          | The patient gives birth to a still born (no signs of life) at or after 22 weeks of gestation is completed  |
| Abortion not otherwise specified (NOS) | Used in cases where spontaneous / elective / therapeutic abortion is not specified. (NOTE: If abortion is performed due to maternal or fetal complications, this case is classified as "Therapeutic abortion") |
| Outcome pending                        | The outcome of the pregnancy is not known (outcome/due date is pending, or queries are outstanding)  |
| Lost to F/U                            | No further information is received regarding pregnancy outcome even after pursuing appropriate number of follow-ups for a case   |

\*\* To be used in the analysis of the secondary outcomes

Source: Manual for Argus Processing - MAP chapter 13 Pregnancy cases, version 10.2, effective 15Jul2021

**Table 7-5 Definition of key fetal/infant outcomes**

| Fetal outcome Argus terminology                | Definition  |
|--|---|
| Normal baby/normal infant                      | Live birth where there is no mention of fetal abnormalities or perinatal complications (regardless of gestational age at birth).  |
| Congenital anomaly major*                      | A congenital abnormality that requires medical or surgical treatment, has a serious adverse effect on health and development, or has significant cosmetic impact.             |
| Congenital anomaly minor**                     | A congenital abnormality that does not require medical or surgical treatment, does not seriously affect health and development, and does not have significant cosmetic impact |
| Congenital/other (structural) abnormality, NOS | Reported congenital anomaly without diagnostic information or other structural anomalies not well described.  |
| Perinatal complication (nonstructural)         | Non-structural perinatal complication of fetus: from 22 weeks of gestation (154 days) to 7 days after birth.  |
| Post-perinatal complication (nonstructural)    | Non-structural post-perinatal complications of fetus: following 7 days after birth.   |
| Abnormality, other (nonstructural)             | Non-structural abnormalities not related to delivery, other non-structural anomalies not well described or anomalies reported as normal variant                               |

| Fetal outcome
Argus terminology | Definition   |
|--|---|
| Fetal death / intrauterine death           | Fetal death confirmed by pre-natal tests, followed by a spontaneous abortion or requiring a therapeutic abortion, or stillbirth.                |
| Blighted ovum                              | Absence of an embryo in a normal-appearing gestational sac visible on ultrasound.   |
| Ectopic pregnancy                          | Implantation of the embryo outside the uterine cavity   |
| Hydatidiform mole                          | Gestational trophoblastic disease where a non-viable fertilized egg or embryo implants in the utero and grows into a mass (instead of a fetus). |
| Infant status unknown                      | Information regarding the infant is not known   |
| Outcome pending                            | The outcome of the fetus/infant is not known (queries are pending or due date is in the future)   |
| Lost to follow up                          | No further information is received regarding pregnancy outcome even after pursuing appropriate number of follow-ups for a case                  |

\*To be used in the analysis of the primary outcome

\*\* To be used in the analysis of the secondary outcomes

Source: Manual for Argus processing - MAP chapter 13 Pregnancy cases, version 10.2, effective 15Jul2021

Table 7-6 lists variables collected via the Infant health status follow-up during first year of life FU checklists that will be used in the evaluation of secondary outcomes if sufficient data is reported.

**Table 7-6 Other variables to be used as secondary outcomes – Infant health status follow-up during first year of life**

| Variable      | Data captured  |
|----------------------|---|
| Infant status        | Living or deceased, if deceased: date of death, age at death, cause of death  |
| Infant demographics  | Gender, age at measurement, weight, length, head circumference  |
| Infant health status | Any malformations identified since birth,
Did reported malformations at or since birth resolve by themselves,
Infection requiring hospitalization** |
| Breastfeeding        | Current breastfeeding status yes/no/weaned;   |
| Developmental delay  | Yes/No, if yes, age at diagnosis, physical, mental/cognitive with free-text comments  |
| Vaccination reaction | Yes/No with free text   |

\*\* To be used in the analysis of the secondary outcomes

### 7.3.3 Other variables

Other variables that are collected via FU checklists and may be used for tabulations of key patient characteristics or further evaluation e.g. stratified analyses are listed in Table 7-7. Any adverse event occurring in the mother during pregnancy related to the pregnancy or in the infant will be collected and captured, per standard PV process, in the event tab in Argus.

Full list of variables to be used in the analyses including any required transformations and calculations will be detailed in the SAP.

**Table 7-7 Other variables and confounders**

| Variable  | Data captured   |
|--|--|
| Country  | Country of report  |
| Maternal Age (years)   | Maternal age (years), continuous and categorical (specific age categories for analysis to be defined in SAP)   |
| Maternal Race/Ethnicity  | Maternal (Caucasian, Black, Asian, Hispanic, Other)  |
| Maternal Height  | Maternal height (cm or in)   |
| Maternal body weight   | Maternal body weight at LMP (kg or lb)   |
| Paternal characteristics   | Age, Race/Ethnicity, Height, Weight, collected as the maternal characteristics detailed above  |
| Number of fetuses  | Number of fetuses (1, 2, >=3)  |
| Other medications taken by the mother during pregnancy   | Medication name, dose/times a day, administration route, indication, start and stop date, trimester of exposure  |
| Contraception  | Yes/no/unknown use of contraception, specific method if known, contraception failure Yes/no/unknown  |
| Prenatal tests   | Test name, date, any abnormal results Yes/No/Not available, free text for test result  |
| Maternal risk factors/conditions that may affect the outcome of the current pregnancy (Yes/No)               | Smoking
Alcohol
Hypertension
Seizure
Eclampsia
Pre-eclampsia
History of infertility  |
| Maternal risk factors/conditions that may affect the outcome of the current pregnancy (Yes/No and free text) | Recreational Drugs
Heart disease
Diabetes
Thyroid disorder
Infections
Environmental or occupational exposure
Fertility treatment
Autoimmune disease
Other, specify |
| Duration of MS disease   | Duration of MS disease   |
| Patient mobile   | Yes/no   |
| EDSS   | EDSS   |
| Relapse just before/during pregnancy   | Yes/No/Unknown; if yes date; treatment given as free-text  |
| Current course of MS   | Primary progressive; Relapsing remitting; Secondary progressive; Other with free text  |

## 7.4 Data sources

Cases reported to the Novartis global safety database will include those cases reported from clinical trials, spontaneous post marketing reports, post marketing observational studies and patient oriented programs. Data on the cases received by Novartis Safety will be captured and processed using the follow-up schedule and questionnaires as described in [Section 7.1](#).

Concomitant or prior medications entered into the database will be coded using the World Health Organization (WHO) Drug Reference List. Medical history/current medical conditions and adverse events, will be coded using the Medical dictionary for regulatory activities (MedDRA) terminology.

Specific data entry conventions are applied, as described in the MAP and PGD, to allow retrieval of exposure, outcome and confounders:

- For exposure, trimesters of administration are entered as tick box by the case processor based on the dose administration information provided in the case.
- Information relative to congenital malformation and pregnancy outcome (Spontaneous abortions, stillbirths, elective terminations) are entered in Argus as birth type and pregnancy outcome as described in [Table 7-4](#) and [Table 7-5](#) based on the case reported verbatim and adjudication (as applicable).
- Low birth weight will be derived from the weight at birth
- SGA, adverse events, serious infections will be identified using MedDRA grouping among events reported in baby.
- Confounders and risk factors will be identified based on the medical history/current medical conditions and adverse events based on MedDRA term groupings.

Cases included in the pregnancy registry study (OMB157G2403), will be excluded from the Kesimpta-PRIM analysis cohorts.

All reports whether submitted by patients or healthcare professionals (HCPs) will be considered.

Even though the primary analysis cohort of interest includes only the prospectively-reported pregnancies associated with maternal exposure during pregnancy or up to 180 days before LMP; all cases outside this cohort will still be processed in the similar manner.

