## **7.2 Setting and study population**

The primary analysis cohort of interest will be the prospectively-reported pregnancies associated with maternal exposure during pregnancy or up to 180 days before LMP.

Retrospective pregnancy cases are defined as pregnancy cases with known pregnancy outcome [i.e. pregnancy outcome (live birth, stillbirth, spontaneous abortion, induced termination)] or known abnormal findings obtained from a prenatal test at the time of initial reporting to Novartis. Considering the high risk of bias resulting from retrospective reports, retrospective pregnancy cases will be processed, analyzed and presented separately from prospective cases. All necessary follow-up information will be presented for those retrospective cases.

Pregnancies with Kesimpta exposure prior to 180 days before LMP or exposure via father will be considered as Kesimpta unexposed cases, but will be processed and presented in a manner similar to the retrospective cases.

[Table 7-2](#) provides details on the prospective vs. retrospective case classification for Kesimpta-PRIM.

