### 7.3.1 Exposure

Trimesters will be defined, based on the dose administered, as follows:

- “Peri-LMP”: LMP- 180 days to LMP,
- “1st trimester”: LMP to LMP+84 days,
- “2nd trimester”: LMP+85 days to LMP+182 days,
- “3rd trimester”: LMP+183 days and beyond.

Cases will be classified by timing of Kesimpta exposure i.e. as “Overall” vs. “Peri-LMP only” vs. “At least 1st trimester” vs. “Only after 1st trimester”.

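### Section 7.4 takes exposure timing from a hand-ticked trimester box although cohort and strata are day-count rules, and states no derivation or check from the start/stop dates collected

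*Protocol*

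**What the plan says.** Section 7.3.1 sets the exposure windows to the day: "Trimesters will be defined, based on the dose administered, as follows". Peri-LMP is "LMP- 180 days to LMP", the first trimester is "LMP to LMP+84 days" and the second is "LMP+85 days to LMP+182 days". Cases are then grouped as overall, peri-LMP only, at least first trimester, or only after first trimester. Section 7.7.1 estimates the malformation proportions overall and in these groups.

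The lower limit of the peri-LMP window also bounds the primary cohort. Section 7.2 states: "Pregnancies with Kesimpta exposure prior to 180 days before LMP or exposure via father will be considered as Kesimpta unexposed cases".

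Section 7.4 gives data entry conventions intended "to allow retrieval of exposure, outcome and confounders". For exposure there is one: "For exposure, trimesters of administration are entered as tick box by the case processor based on the dose administration information provided in the case".

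The pregnancy outcome checklist (Table 7-3) records for the mother's medications: "Name, dose, route of administration, start/stop, trimester of exposure". Section 7.6 says checklist data are entered in the safety database.

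**The concern.** A rule written in days is best applied by subtracting dates. Here the named source is a category chosen by hand, case by case. The protocol does not say that a program applies the windows to the dates, which of the two prevails if they differ, or that they are compared.

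Two things depend on the result. The first is whether a pregnancy counts in the primary cohort or is set aside as unexposed. The second is which timing group it joins for the primary endpoint. An error near a cut-off would move a pregnancy across one of these lines, and two processors could read the same case differently. The protocol invites this at one point, because a dose on day LMP satisfies both the peri-LMP and the first-trimester definition.

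**Working it through.** **Which cut-offs matter.** I read the box as including a peri-LMP option, because section 7.3.1 lists that window among its trimesters.

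| Cut-off | What it decides |
|---|---|
| LMP-180 | Inside or outside the primary cohort |
| LMP | Peri-LMP only, or at least first trimester |
| LMP+84/85 | At least first trimester, or only after it |
| LMP+182/183 | Second or third trimester; separates none of the four analysis groups |

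Only the first three matter here.

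**Day LMP.** Let d be the day of dosing counted from LMP. Peri-LMP is -180 ≤ d ≤ 0 and first trimester is 0 ≤ d ≤ 84, so d = 0 satisfies both. A woman whose last dose fell on that day can be placed in either group.

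**Safeguards in the text.** Section 7.8.1 provides training for case processors and additional checks on core data elements, without mentioning a comparison of box and dates. In Annex 2, the comment under section 5 of the ENCePP checklist says no further measures are planned to ensure validity of measurement. Item 7.3 of that checklist points to section 7.9 for information bias, but section 7.9 does not discuss misclassified exposure timing.

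**The plan's own power figure.** Inputs from section 7.5 and Table 7-8 are N = 500, P0 = 0.03, P1 = 0.06 and a two-sided exact binomial test at 0.05.

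- Upper limit: P(X ≥ 23 | 0.03) = 0.0306 exceeds 0.025, and P(X ≥ 24 | 0.03) = 0.0179 does not. Reject at 24 or more cases.
- Lower limit: reject at 7 or fewer. The actual two-sided alpha is 0.0347.
- Power at 0.06 is 0.8926, as in Table 7-8. The other eight rows also reproduce to four decimals.

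**Illustration of size.** Assume a share f of the 500 was in truth exposed only before LMP-180 and carries the 3% background prevalence. The cohort prevalence becomes 0.06 - 0.03 × f.

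| f | Prevalence | Power |
|---|---|---|
| 0 | 0.0600 | 0.893 |
| 2% | 0.0594 | 0.882 |
| 5% | 0.0585 | 0.865 |
| 10% | 0.0570 | 0.832 |
| 15% | 0.0555 | 0.794 |
| 20% | 0.0540 | 0.751 |

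The protocol gives no value of f. For scale only, suppose last doses were spread evenly over the 180-day peri-LMP window. Then 7/180 = 3.9% of them would lie within 7 days of one end, and 10/180 = 5.6% within 10 days. These are shares near a cut-off under two assumptions (the even spread and the 7 to 10 days). They are not error rates of the box. They also refer only to women whose last dose fell in that window, so they are a smaller share of the whole cohort.

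**The case against.** The strongest reply is that this belongs to the SAP, which is not at hand. Section 7.3.3 leaves the variable list, transformations and calculations to it, and a program may well be specified there. This answers part of the point. What remains is that section 7.4 itself names the exposure source, and in the same list says that low birth weight will be derived from birth weight. Derivation is stated for that variable and not for exposure.

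A second reply is that the box is filled from the same dose information a program would use, by trained staff, with additional checks. That stands, and it limits the point to a risk.

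Three stronger readings are tempting, and the protocol supports none of them:

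- **That pregnancies are in fact misclassified.** Nothing shows that they are.
- **That intervals from dose to LMP cannot be derived.** Start/stop is collected and checklist data enter the database. The interval would be out of reach only if these dates, or LMP, were kept solely as narrative. Section 7.3.2 says some variables are free text only but does not say which.
- **That the box stays fixed when dating is revised, or is ticked with the outcome in view.** Section 7.3 has exposure data collected at enrolment and at four later points. Primary-cohort cases are reported before the outcome is known. The outcome checklist does carry exposure and anomalies on one form, so influence is conceivable, but nothing says when the box is set.

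The remedy also has limits. Table 7-3 lists start/stop and not a date for every injection, and section 7.9 concedes that reports are often incomplete.

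**Conclusion.** The point holds as a weakness in the stated method. A manual category is the named source for rules that are day counts, the dates needed to apply those rules are on the checklist, and no derivation or cross-check is stated. Cases near LMP-180, LMP or LMP+84/85 may therefore be misclassified.

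The size is unknown. The effect on the overall estimate is probably modest: with 5% of the cohort (25 of 500) wrongly included at background prevalence, power moves from 0.893 to 0.865. This rests on the assumed f, on the 6% alternative for truly exposed pregnancies, and on errors in one direction only. The effect on the timing strata cannot be computed, because their sizes are not given. No stated figure in the protocol is wrong on this account. This is a desirable improvement, not a flaw that endangers the study.

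**What to change.** In section 7.4, state that:

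- primary-cohort membership and timing stratum are derived by program from Kesimpta start/stop dates and the latest LMP, or an LMP calculated from the EDD;
- the tick box is used only when dates are missing or partial, and those cases are flagged;
- each report gives the number of cases where the derived and ticked categories disagree.

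In section 7.3.1, assign day LMP to one window only. Deriving the windows from dates would not by itself remove that overlap.

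The cost is a short extra derivation in the SAS programs, from items the checklists already collect. With no misclassification the power stays at 0.8926, and no sample size changes. The remaining drawback is that the tick box still decides cases with incomplete dates, and their number is unknown until the flag is reported.

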#### **7.4.1 Data linkage in Novartis global safety database**

As per the MAP, individual cases of mother and fetus/infant or father and fetus/infant are linked with each other in Argus and can be identified for data extraction.

#### **7.5 Study size/power calculation**

This study is descriptive in nature and will last for a maximum of 10 years from market authorization or until 500 prospectively reported live births with known status of malformations are included in the analysis, whichever occurs first.

The prevalence of major congenital malformations is reported as 3% of live births in the US ([CDC 2018](#)) and 2.6% of live births in Europe ([EUROCAT 2019](#)). Worldwide about 6% of all newborn infants have serious birth defects of genetic or partially genetic origin and the annual prevalence of congenital malformations was 3.6% of births ([Christianson et al 2006](#)).

[Table 7-8](#) provides the power to detect various prevalence differences depending on the background prevalence and the number of live births (i.e. sample size).

For example, if 500 live births are included, assuming a background prevalence of 3% (i.e. the prevalence of birth defects reported in US ([CDC 2018](#))), this study will have 89% power (two-

sided binomial exact test for one sample proportion, target  $\alpha$  set at 0.05) to detect a 3% increase in prevalence over the background prevalence (i.e. an observed prevalence of 6%).

After 10 years, if the targeted sample size (500) is not obtained or if a conclusion cannot be drawn with the number of cases available, then the potential risk of pregnancy exposure will be considered very low. At that point, the Kesimpta-PRIM study will be planned to be discontinued following discussion with the health authorities.

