## 6 Research question and objectives

The overall objective of the Kesimpta-PRIM study is to evaluate data on a) pregnancy and infant outcomes related to Kesimpta exposure in MS patients immediately before (up to 180 days before last menstrual period (LMP)) and during pregnancy; and b) infant outcomes at birth and 12 months post-delivery. The study utilizes data collected on pregnancies reported to the Novartis global safety database and followed up via the PRIM process ([Geissbühler et al 2020](#)).

The below objectives will be assessed focusing primarily on prospectively reported pregnancies associated with maternal exposure. ‘Exposure to Kesimpta during pregnancy’ will be defined using Kesimpta’s pharmacodynamic effect and taken as exposure to Kesimpta immediately before (i.e. up to 180 days before last menstrual period (LMP)) and during pregnancy.

The findings from this study will be used to evaluate the potential risk of reproductive toxicity, according to the Risk Management Plan (RMP).

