## 7.9 Limitations of the research methods

The limitations of PRIM are detailed by [Geissbühler et al \(2020\)](#) and are consistent with those of voluntary post marketing report systems: under reporting, and a potential for more missing or incomplete information than in a clinical study. Spontaneous report data are collected passively relying on healthcare professionals and patients to recognize suspected adverse outcomes, collect and collate relevant information, and submit reports in the required format. Hence, the information received is often insufficient or incomplete. To reduce the potential for selection bias due to loss to follow-up (a recognized limitation of voluntary reporting systems), contact attempts via multiple contact modalities are systematically and repeatedly performed under the PRIM processes. In addition, prospective cases (where pregnancy outcome is unknown at the time of reporting) and retrospective cases will be evaluated separately given the risk of selective reporting of adverse outcomes in retrospective reporting.

A direct comparison between prevalence estimates of congenital malformation and other outcomes obtained through PRIM with external reference in the general populations is hampered by potential differences in data collection methods. Interpretation of the results of these comparisons is therefore limited. Nevertheless, the results can be put in context with a range of estimates from the general population coming from different data sources with a focus on those which use similar data collection methods as PRIM ([Geissbühler et al 2020](#)).

To evaluate the impact of exposure on the pregnancy outcomes further, exposure is stratified as exposure during peri-LMP only vs exposure only after 1st trimester. These categories may, however, be subject to selection bias. The group “exposure during peri-LMP only” excludes pregnancies with normal outcomes without any assessment of drug exposure duration (i.e., throughout the entirety of the pregnancy). On the other hand, the group “exposure only after 1st

trimester” could be subject to immortality bias. By construction, the category would not capture any event prior to 1st trimester of exposure.

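### Section 7.5 turns a shortage of data after 10 years into a finding that the risk is very low, whatever malformation proportion is observed

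*Protocol*

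**What the plan says.** Protocol section 7.5 runs the study for at most 10 years from market authorization or "until 500 prospectively reported live births with known status of malformations are included in the analysis, whichever occurs first". It then says what follows if the study falls short. The first condition is that the target of 500 is not reached. The second condition, with the consequence that applies to both, reads "if a conclusion cannot be drawn with the number of cases available, then the potential risk of pregnancy exposure will be considered very low". The next sentence adds that "the Kesimpta-PRIM study will be planned to be discontinued following discussion with the health authorities".

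Other sections bear on this:

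- Section 5 says that safety in pregnancy and lactation is listed as missing information in the Risk Management Plan because human data are limited.
- Section 6 gives the use of the results: "The findings from this study will be used to evaluate the potential risk of reproductive toxicity".
- Section 7.9 names as limitations of the source "under reporting, and a potential for more missing or incomplete information than in a clinical study".
- Section 7.7 requires exact (Clopper-Pearson) 95% intervals where intervals are presented, and section 7.7.1 applies 95% intervals to the malformation proportions.

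**The concern.** Two conditions joined by *or* lead to one conclusion. One is a count of live births below 500, the other is an inability to conclude. Neither looks at how many malformations were seen. The less the study can say, the more surely the protocol assigns it a reassuring reading.

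The study exists because information is lacking. If it ends with too little information, the honest result is that the question is still open. The rule instead commits the final report in advance to an interpretation that its own estimate and interval may not support, or may contradict. The error runs in one direction only, towards reassurance, and it concerns the primary safety outcome.

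**Working it through.** **Inputs, all from the protocol.** Background prevalence 3% (section 7.5: "The prevalence of major congenital malformations is reported as 3% of live births in the US"); planning alternative 6%; two-sided exact binomial test at 0.05 (section 7.5, Table 7-8); target 500 live births; Clopper-Pearson 95% intervals (section 7.7). The number of live births that will be available at 10 years is not given. The value 400 is a row of Table 7-8; 499 and 100 are assumed for illustration.

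**Step 1: reproduce the plan's power.** With equal tails of at most 0.025 under 3%, the rejection region at n = 500 is X ≥ 24 or X ≤ 7.

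- P(X ≥ 24 | 3%) = 0.0179, while P(X ≥ 23 | 3%) = 0.0306, so 24 is the upper critical value.
- P(X ≤ 7 | 3%) = 0.0168, while P(X ≤ 8 | 3%) = 0.0354, so 7 is the lower one.
- Power = P(X ≥ 24 | 6%) + P(X ≤ 7 | 6%) = 0.8926.

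This is the value in Table 7-8, and the other eight rows also reproduce to four decimals. The power table is not at fault.

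**Step 2: the first condition on its own (fewer than 500 live births).** The interval for x malformations in n live births is

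- lower limit = 0.025 quantile of Beta(x, n − x + 1)
- upper limit = 0.975 quantile of Beta(x + 1, n − x)

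| Malformations / live births | Proportion | Exact 95% CI | Label under section 7.5, read literally |
|---|---|---|---|
| 24/400 | 6.0% | 3.9% to 8.8% | very low |
| 40/499 | 8.0% | 5.8% to 10.8% | very low |

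Both lower limits exceed 3%. At n = 400 the upper critical value of the protocol's test is 20, so 24 would also be significant. The rule gives the same label because n is below 500.

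**Step 3: the second condition (no conclusion possible).** Take an assumed 100 live births.

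| Malformations / live births | Proportion | Exact 95% CI |
|---|---|---|
| 3/100 | 3.0% | 0.6% to 8.5% |
| 6/100 | 6.0% | 2.2% to 12.6% |

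The first sits at the background value and the second at the planning alternative. Both intervals contain both 3% and 6%, so neither result separates no excess from a doubling. The rule calls both very low.

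**Step 4: the exposure reading.** The words could instead mean that few pregnancies are exposed. Set against the rest of the text:

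- An inconclusive malformation result says nothing about how often exposure occurs, so this reading does not fit the second condition.
- The count in the first condition covers only prospectively reported live births with known malformation status. It leaves out retrospective cases, other pregnancy outcomes and cases lost to follow-up.
- Registry cases are excluded (sections 7.2.2 and 7.4).
- Section 7.9 concedes under-reporting.

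A low value of this count therefore does not show that exposure is rare.

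**The case against.** The best defence is the exposure reading. Where the protocol means harm it speaks of risk to the fetus (section 5) or of reproductive toxicity (section 6), and the abstract notes that contraception is recommended. The authors may have meant that, if so few cases arise in 10 years, exposure is rare and the study can end. That is a plausible intent for the low-count condition. It fails for the other condition, and the source cannot support it (step 4). At best the sentence is ambiguous, and it still needs correcting.

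Second, other provisions apply whatever the sample size: proportions with 95% intervals, comparison with external data for the primary cohort, nine annual interim reports, submission of interim and final reports to EMA, external adjudication, and a steering committee that reviews data and interpretation across the Kesimpta pregnancy studies. A reader might infer from the rule that a real malformation signal would be closed out unseen. The documents do not support that, because regulators would see the figures every year. What these provisions do not do is remove a conclusion written in advance. The discussion with health authorities does not do so either, since it is attached to discontinuation and not to the label.

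Third, a reader might take the probability of missing a true doubling at small n (for example 1 − 0.25 = 75% at an assumed 100 live births) as the rule's error rate. It is not. The protocol's ENCePP checklist says that no hypotheses are tested, the inability to conclude is nowhere defined by significance, and read literally every result below 500 falls under the rule, significant or not. Such figures describe power only.

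**Conclusion.** The point holds: the label of very low risk does not follow from either condition and should not stand. It rests on the literal text of section 7.5. The intervals show its size. An observed 6.0% with a lower limit of 3.9% (24/400) would be labelled very low, and so would a result compatible with anything from 0.6% to 8.5% (3/100). The second example depends on an assumed number of live births; the logical defect does not depend on any particular number. The consequence is limited by the regular reporting and outside review, so the finding is a wrong pre-specified interpretation, not a hidden signal. The power calculation itself is correct.

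**What to change.** Delete the inference and replace the two closing sentences of section 7.5 with text such as:

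> If, at 10 years, there are fewer than 500 live births or the data do not allow a conclusion, the observed proportion and its exact 95% CI will be reported, together with the largest prevalence that the upper limit does not exclude. Where the interval does not support a conclusion, the result will be described as inconclusive. A low number of reports will not be interpreted as low risk or as low exposure. Discontinuation of the study will then be discussed with the health authorities.

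This covers both conditions and keeps the discontinuation step. The estimate and interval are already planned; what is new is stating the largest prevalence not excluded and describing an inconclusive result as such. No pass/fail threshold is needed in a study declared descriptive, and the classification in the Risk Management Plan need not be settled here.

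The cost is a short rewording, with no new data. The downside is a less favourable default conclusion for the sponsor.
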